Figure 3 below represents the initial model we plan to test for the catastrophizing mechanism variable, providing that it evidences at least a small effect for change for at least one treatment condition during the first two weeks of treatment. However, the model will be simplified (by removing treatment condition as a predictor, and the paths associated with treatment condition) if non-significant treatment effects are found. Up to two additional SEM models will also be tested, with non-judgment and activity level as the foci. Below we describe the specific steps planned to address the study aims and test the primary study hypotheses.

Figure 3. Initial model testing the mechanism role of pain catastrophizing during treatment

Step 1. Ensure at least small time effects (slope) in the early mechanism variables for at least one of the treatment conditions (a requirement for that variable to be considered as a possible mechanism).

- (1) We will perform an initial one-way Analysis of Variance (ANOVA) comparing the pre- to mid-treatment mechanism slopes between the three treatment conditions, separately for each of the three mechanism variables, with a goal of identifying the effect (i.e., Eta squared, η^2) associated with any between group differences in early changes in mechanism variable. If this effect size is < 0.01 , this would indicate a less than small between-group difference in the amount of early treatment change for that mechanism;

this would be interpreted to mean that all three treatment conditions had a similar effect on early treatment change in the mechanism variable.

- (2) In the event that a less than small between condition effect is found, we would then examine the pre- to mid-treatment time effect of this mechanism collapsed across groups to see if this mechanism changes from pre- to mid-treatment (i.e., early treatment). If this effect size (η^2) associated with this time effect collapsed across groups for any mechanism variable is less than 0.01 (representing a small time effect) then there would be evidence that the variable in question is unlikely to act as a mechanism, because at least some change over time early in treatment for that variable, on average, is needed for it to serve as a mechanism.

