- (3) If less than small effects emerge for both the between-group effects on the early mechanism slope *and* for the time effect (i.e., average slope), this would be interpreted to indicate a lack of early change (in any treatment condition) on the mechanism variable. In this instance, that mechanism variable would not be tested in a subsequent SEM. If *either* of the effect sizes are equal to or larger than 0.01 (indicating a small or larger time effect, on average) or a small or large Group X Time effect emerges (indicating at least a small group effect on early change in mechanism), then we will proceed to Step 2 for that mechanism variable.

Step 2. Test the model presented in Figure 3 for any mechanism variable that met the Step 1 conditions described above.

- (4) First paths a_1 and a_2 will be tested. The a_1 and a_2 coefficients represent the strength of the predictive relationships from the two dummy IVs¹ to early treatment slope in catastrophizing (i.e., to evaluate the impact of treatment condition on early treatment changes in catastrophizing). Together, these tell us if treatment condition had a direct effect on the early treatment slope in the mechanism variables. If both of these coefficients are non-significant (consistent with the Shared Mechanisms Model) they will be eliminated from the final SEM. If either or both of these pathways are statistically significant, this will be interpreted to mean that there is a between-treatment condition difference in early change in the mechanism variable being evaluated, and these effects will be retained in the model.
- (5) In the case of at least one statistically significant a coefficient, we will perform planned post-hoc ANOVA models for each of the three treatment groups to understand these differences and to determine if the findings are consistent with the Specific Mechanisms Model. For example, if catastrophizing is uniquely targeted by CT, we would anticipate a significant treatment condition effect (in either or both of the two a coefficients) on early catastrophizing slope, with post hoc tests indicating larger pre- to mid-treatment decreases in catastrophizing for the CT condition than the MM or AS interventions. However, the full test of the Specific Mechanisms Model also takes into account the b path, described below.

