¹ In the proposed SEM, treatment condition (i.e., which of three treatments the participant is assigned to) is represented by two variables: "CTvsOther" (coded as "1" if the participant is assigned to the CT condition, "0" if not) and "MMvsOther" (coded as "1" if the participant is assigned to the MM condition, "0" if not). These two dummy variables are exogenous and have a correlation of $r = .50$ (if groups are of equal size). When considered in the same model (i.e., when controlling for the other), the two variables contain information about all three treatment conditions.

[figure not shown]
(6) In order to establish a mechanism effect on outcome (i.e., that cognitive content, cognitive process, or activity level predicts subsequent change in pain interference) we will next test for significance of the *b* coefficients. We will test the *b* coefficient for significance across each of the three mechanism variables (i.e., three significance tests, one per SEM model). Any *b* coefficients that are not significant indicate that early change in that mechanism variable is not associated with late change in pain interference, indicating a lack of support for it as a mechanism variable in treatment. A significant *b* coefficient will be interpreted as evidence supporting early treatment change in the mechanism variable in question as explaining late treatment change in pain interference.

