As indicated, up to three SEMs (one for each mechanism) will evaluate and test for significance of the *a* and *b* coefficients for each mechanism variable that met the Step 1 assumptions described above (i.e., that evidenced at least a small early slope or larger, for at least one of the treatments). The combination of a treatment effect on the mechanism variable (coefficient *a*) and a significant *b* coefficient for a particular mechanism variable (indicating that early change in the mechanism variable predicts a late change in outcome), with *post hoc* tests linking each treatment to its targeted mechanism variable (i.e., CT, MM, and AS having the largest effects on cognitive content, cognitive process, and activity level, respectively) would support the Specific Mechanisms Model. A significant *b* coefficient in light of non-significant *a* coefficients (i.e., the mechanism plays a role in outcome, but all three treatments have a similar impact on the mechanism variable) would support a Shared Mechanisms Model. Thus, together, the significance levels of the *a* and *b* coefficients will address the study aims. In short, the results of the (maximum) six planned statistical tests (i.e., whether or not there are between-group differences in the three early mechanism slopes, and the significance level of the three *b* coefficients) will allow us to evaluate if the three mechanism variables play a role in treatment outcome, and whether this role is shared between the treatments or unique to a subset of them.

Exploratory Moderation Analyses

We also plan to conduct a preliminary test of the LAE model. Specifically, SEM will be used to evaluate the extent to which baseline catastrophizing, activity levels, and non-judgment are respectively associated with response to CT, AS, and MM. Figure 4 below illustrates the statistical approach that we propose to use to evaluate the LAE model. For illustrative purposes, only the role of baseline catastrophizing moderating response to treatment is depicted. As per the above models, the treatment condition variable is represented by two variables: "CTvsOther" (coded as "1" if the participant is assigned to the CT condition, "0" if not) and "MMvsOther" (coded as "1" if the participant is assigned to the MM condition, "0" if not). When considered in the same model (i.e., when controlling for the other), the two variables contain information about all three treatment conditions.

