Figure 4. SEM model evaluating the "Limit" component of the LAE model

In the model depicted in Figure 4, while significant change in outcome from pre- to post-treatment is expected, it is anticipated that the effect of treatment condition on outcome will be non-significant (i.e., we anticipate that all three treatments will be associated with similar pre- to post-treatment improvements in pain interference, as reflected by non-significant a_1 and a_2 coefficients). However, the LAE model predicts that the post-treatment pain interference score, when controlling for pre-treatment pain interference, will be significantly associated with baseline levels of pain catastrophizing (i.e., path b in the model). We will also test the b coefficient for significance across each of the three moderating variables. The extent to which the effect of the baseline moderator variable predicting outcome varies as a function of treatment will then be evaluated (i.e., the c_1 and c_2 coefficients in Figure 4). These two pathways from condition to path b in the model, when combined and examined as a single parameter, if significant, will indicate the presence of a Treatment \times Moderator interaction. In the event that this interaction effect is identified, post hoc tests will be conducted separately for each treatment condition. Continuing with the example shown in Figure 4, if baseline catastrophizing is found to be negatively associated with subsequent outcome, and this effect is stronger in CT than in MM and AS, then this will be interpreted as lending support for the predictions made with respect to the “Limit” component of the LAE model.

Additional Exploratory Analyses

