Assuming at least medium effects (i.e., $rs \geq .30$ and/or $ds \geq .50$), we can then compute the sample sizes needed to detect significant effects for the planned primary analyses, using the Hochberg and Benjamini procedure to control for alpha inflation in these analyses. This alpha control procedure involves putting the significance levels of the six planned primary analyses in ascending order, and matching them to the actual significance levels obtained with the six analyses, also placed in ascending order. The number needed to detect significant effects for each of these analyses is presented in Table 5, below, using the tests for the three direct mediation effects of the mechanism variables for three of these analyses, and a test for the three Treatment Condition X Mediation (representing moderated mediation) effects for the other three analyses, assuming at least medium effects for each of these effects. Sample size estimates needed to detect the primary mediation effects were conducted based on the joint significance method of testing mediated effects, using the PowMedR program in R Version 3.0.2 statistical software with the following assumptions: (1) alpha levels consistent with the Hochberg and Benjamini procedure (see Table 5, below); (2) power of 0.80; and (3) at least medium effects. Power calculations for the interaction (mediated moderation) analyses were conducted using G*Power3 with the same assumptions.

Table 5. Sample size estimates for the six planned analyses, assuming medium effects for the causal paths (a and b) and at least a medium interaction effect (f^2) for the three planned Treatment Condition X Mediation effects tests

Alpha	Power	Effect size path a	Effect size path b	Interaction effects	n-required / n-planned
0.050	0.80	Medium ($r = 0.30$)	Medium ($r = 0.30$)		109 / 240
0.025	0.80	Medium ($r = 0.30$)	Medium ($r = 0.30$)		129 / 240
0.017	0.80	Medium ($r = 0.30$)	Medium ($r = 0.30$)		140 / 240
0.013	0.80			Medium ($f^2 = 0.15$)	93 / 240
0.010	0.80			Medium ($f^2 = 0.15$)	98 / 240
0.008	0.80			Medium ($f^2 = 0.15$)	102 / 240

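### D6s and D6u list different sets of six primary tests, and the Treatment Condition X Mediation tests sized in D6u appear in no written Aim 1 step or decision rule in D6s

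*Combined protocol and SAP*

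**What the plan says.** **D6s, Aim 1 steps and rule.**
- Step 2 (4) tests the paths from condition to early mechanism slope (a1, a2): "If both of these coefficients are non-significant (consistent with the Shared Mechanisms Model) they will be eliminated from the final SEM". The text introducing Figure 3 likewise simplifies the model "by removing treatment condition as a predictor, and the paths associated with treatment condition".
- Step 2 (5) adds post hoc comparisons of the mechanism slope and notes that "the full test of the Specific Mechanisms Model also takes into account the b path, described below".
- Step 2 (6) then tests the b "coefficient for significance across each of the three mechanism variables (i.e., three significance tests, one per SEM model".
- Specific is supported by a treatment effect on the mechanism, post hoc tests tying each treatment to its target, and a significant b. A significant b with non-significant a is the other case: "all three treatments have a similar impact on the mechanism variable) would support a Shared Mechanisms Model".
- The closing count of at most six tests is "whether or not there are between-group differences in the three early mechanism slopes, and the significance level of the three" b coefficients.

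**D6u.** The six tests are three direct mediation effects, sized by joint significance of a and b, and "a test for the three Treatment Condition X Mediation (representing moderated mediation) effects for the other three analyses". The Table 5 title calls the latter planned. The text after the table rests its power argument on condition entering as an interaction.

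**Hypotheses and aim.** Hypothesis 1c has two parts: condition affects early change in the mechanism, and different mechanisms predict outcome in different arms. The opening of D6s asks whether the associations are shared or unique to some treatments.

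**The concern.** Two competent analysts could run different primary families from this document, with different tests entering the Hochberg and Benjamini adjustment. Shared against Specific is the main conclusion of the trial, so the choice matters.

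The second part of Hypothesis 1c and the shared-or-unique aim are questions about whether b differs by arm. The D6s rule uses one b per model and cannot answer them. It also removes condition from the model when a is non-significant, after which a condition-by-b test cannot be run in that model.

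The authors do write out such a test elsewhere. In the exploratory moderation model, c1 and c2 are tested jointly: "These two pathways from condition to path b in the model, when combined and examined as a single parameter, if significant". There, however, the predictor is a baseline moderator and not early change.

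**Working it through.** **1. Reproduce Table 5.**
- Rows 4-6: noncentral F for an R-squared increase, 2 numerator df (two condition dummies times the mechanism), lambda = f2 x N, f2 = .15, power .80. At alpha .013, .010 and .008 this gives 93, 98 and 102, exactly as printed. One numerator df gives about 78, 82 and 86; three gives about 104, 109 and 114.
- Rows 1-3: joint significance, power(a) x power(b), r = .30 on each path. At alpha .050, .025 and .017 Fisher z gives 111, 131, 142 and noncentral t gives 107, 126, 137, against 109, 129, 140 printed.

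**2. Match the lists.** Joint significance needs both a and b, so the D6s a and b tests are the components of rows 1-3. Rows 4-6 match nothing in the D6s list.

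**3. Power at N = 240, alpha .05/6 = .0083.** Slope test at r = .30 (f2 = .09/.91 = .099): .97. b test at r = .30: .99. Interaction at f2 = .15: .998.

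**4. What f2 = .15 means.** Suppose b holds in one arm and is 0 in the other two, with slopes standardised within arm. The variance of b across arms is b²/3 - b²/9 = 2b²/9, and the mean residual variance is 1 - b²/3, so f2 = (2b²/9)/(1 - b²/3).
- b = .30: .0200/.9700 = .0206
- b = .57: .0722/.8917 = .0810
- Setting f2 = .15 gives b² = .15/(.2222 + .05) = .551, so b = .74

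The associations that D6u cites have magnitudes .30, .35 and .57. Interaction power for this pattern (2 and 234 df, lambda = 240 x f2):

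| b | alpha .05 | alpha .0125 |
|---|---|---|
| .30 | 49% | 29% |
| .35 | 64% | 42% |
| .50 | 93% | 83% |
| .57 | 98% | 94% |

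(.05/4 = .0125, printed as .013 in Table 5.)

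**5. Simulate the D6s rule.** Assumptions: 80 per arm, unit-SD slopes, no measurement error, one mechanism, CT as target arm. Specific requires a1 or a2 significant, b significant, and the target arm above each other arm at p < .05. That post hoc rule is assumed, because D6s does not state one. Repeated runs agree within about 1 point.
- *b = .30 in every arm, target arm shifted by d = .50.* Specific is declared in about 79% of trials at .05 and 67% at .0125. If a significant interaction and a significant, largest target-arm b are also required, this is about 1% at .05.
- *Equal a, b in one arm only.* At .05, Shared is reported in about 32% (b = .30) and 76% (b = .57).
- *Hypothesis 1c fully true, d = .50, b = .30.* Adding the interaction to the pooled-b rule lowers correct Specific verdicts from about 27% to 13% at .05, and from 12% to 3% at .0125. At b = .57 the change at .05 is 67% to 66%.

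**The case against.** The best defence is that the intent is on record: D6u plans the interaction, Step 2 (5) promises a fuller test of the Specific model, and Figure 3, which is not reproduced in the text available, might draw a path from condition to b. This limits the point to the written text. It does not remove it, because the count that closes the D6s section excludes the interaction whatever the figure shows.

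A reader might also infer more than the documents support:
- *That the slope tests are unsized.* Path a is part of Table 5 rows 1-3. Only a separate 2-df between-arm row is missing.
- *That reporting Shared when a is equal and b exists in one arm is an error under Hypothesis 1c.* The first part of 1c fails in that case, so 1c does not call for Specific. The gap is against the shared-or-unique aim in D6s.
- *That Hypothesis 1b defines Shared by equal effects on the mechanism.* It states an implication: if mechanisms are shared, condition effects on them will be small. It is not a definition.
- *That the trial is too small.* At the medium effects Table 5 states, 240 suffices for either set of six.

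It is fair to add that the 79% depends on the assumed post hoc rule and on a between-arm d of .50. That is the plan's stated floor for a medium d, but the effects it cites are mainly pre-post changes.

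**Conclusion.** The point stands as an internal contradiction with consequences for the primary conclusion. The two sections fix different primary families, and a test that D6u plans and sizes has no place in the written Aim 1 steps or rule. Under the assumptions shown, the D6s rule would usually declare Specific when only the effect on the mechanism differs and b is the same in all arms.

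The arithmetic of Table 5 is sound. The claim of being well powered needs qualifying for the interaction, because f2 = .15 corresponds to b of about .74 in one arm and none in the others, above every association the plan cites. Applying those cited associations as arm-specific values of b is an assumption.

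**What to change.** 1. State one identical closed list of primary tests, with the size of the multiplicity family, in D6s, D6u and Table 5.
2. Add to the D6s Aim 1 steps the 2-df test of condition by early mechanism slope on late pain interference, in the c1/c2 form of the exploratory section. Run it before condition is dropped from any model, and report b by arm with confidence intervals.
3. Amend the rule so that Specific also requires this interaction in the hypothesised direction, and so that a significant interaction with equal a is not reported as plain Shared.
4. Align Table 5 with the chosen list, show interaction power over b = .30 to .57, and qualify the well-powered statement.
5. Say whether Hypothesis 2c, which defines Specific for Aim 2 by effects on the mechanism alone, is meant to omit the b part.

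Date the change before data lock. Replacing Table 5 rows 4-6 with the D6s tests would also align the lists, but would leave the second part of Hypothesis 1c untested. A nine-test family, target-arm b in place of pooled b, and a fuller verdict table are options with their own trade-offs.

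**Cost.** Wording, a revised table, and one further test per mechanism on data already collected. If the three interactions join the three slope and three b tests, the strictest step moves from .05/6 = .0083 to .05/9 = .0056. Slope power at d = .50 then goes from 75% to 71% at that step, and interaction power at b = .30 from 24% to 20%. At b = .30 the question of whether b differs will often stay unresolved: 80% interaction power would need about 471 participants at .05 or 650 at .0125. The plan should state this, and the fall in correct Specific verdicts shown above, as limits.

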Hypothesis 1c: The Specific Mechanisms Model hypothesizes that if changes in content, process, and activity level are mechanisms specific to CT, MM, and AS, respectively, then treatment condition will have a significant effect on early changes in the mechanism variables (i.e., the effects of the three treatments on the three mechanism variables will be different, with CT having the largest effects on early treatment decreases in catastrophizing, MM having the largest effects on early treatment increases in non-judgment, and AS having the largest effects on early treatment increases in activity level). Further, later improvement in the primary outcome will be predicted by different mechanism variables as a function of treatment condition; that is, late treatment changes in pain interference will be substantially and uniquely predicted by early treatment changes in: (1) cognitive content (i.e., pain catastrophizing) in CT but not in MM or AS; (2) cognitive process (i.e., non-judgment) in MM but not in CT or AS; and (3) activity level in AS but not in CT or MM, in addition to each mechanism variable significantly predicting the primary outcome (Specific Mechanisms Model).

We also predict that change in the mechanism variables will precede and predict change in outcome, but not vice versa.

A2b. Secondary Aim and Hypotheses

Aim 2: Evaluate the post-treatment mechanisms that explain relapse, maintenance, and continued gains.

As a secondary aim, this study will also evaluate the post-treatment mechanisms that explain relapse, maintenance, and continued gains associated with these treatments [**Aim 2; Secondary**]. The Shared (Hypothesis 2a) and Specific (Hypothesis 2b) Mechanisms Models will also be applied to data collected via EMA and ActiGraph daily during the 4-weeks post-treatment to better understand the post-treatment mechanisms that underlie maintenance of gains and relapse.

Hypothesis 2a: Early post-treatment changes (i.e., post-treatment to 2-weeks post-treatment) in cognitive content, cognitive process, and activity level will be significantly associated with late post-treatment changes (i.e., 2-weeks post-treatment to 4-weeks post-treatment) in pain interference.

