Thus, by employing the analytic models experiment-wise, and by integrating treatment-condition into the model(s) as an interaction effect (rather than running separate analyses for each treatment condition), we will be able to take advantage of the power afforded by running the entire sample of participants ($n = 240$) through the planned tests. This, combined with the less stringent Hochberg and Benjamini type-I error adjustment (alpha-correction), has left us well-powered to detect the hypothesized effects. That said, we plan to enroll 300 participants with a goal of obtaining complete data for 240 participants ($n = 80$ per condition) to ensure that we will be able to compute reliable effect sizes for the planned secondary analyses (the results of which will be discussed in terms of their effect sizes and not significance levels, although significance levels and associated confidence intervals will also be reported).

HUMAN PARTICIPANTS SECTION

E. Risk to Participants

E1. Human Participants Involvement and Characteristics

We plan to enroll up to 300 participants into the study. Our primary source of potential participants for this study is all individuals who have been seen as patients at either Harborview Medical Center (HMC) or the University of Washington Medical Center (UWMC), and who meet study eligibility criteria.

If needed and required, we will also recruit from other modalities. These other modalities include through flyers/brochures/advertisements in various clinics and hospital spaces, the UW Medicine Newsroom, clinician and participant referrals, social media/online recruitment, and nationally, if needed.

E2. Sources of Materials

Several sources of information will serve as data for the study, including medical record reviews, self-report assessments and interviews, ActiGraph activity data, and audio-recorded treatment sessions (to be used for supervision and determination of adherence and fidelity). The study design involves non-invasive procedures.

The data described will be collected solely for research purposes.

E3. Potential Risks

It is anticipated that participants, irrespective of treatment condition, will experience significantly more benefits than risks from participation in this study. Although the methods and interventions have limited participant risks, several safeguards will be implemented to reduce these.

E3a. General / Reaction to Assessments

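### Table 5's interaction effect of f² = 0.15 is not derived and, under Hypothesis 1c, needs a one-arm r of about .74; at the plan's r = .30 floor, power at N = 240 would be 24–29%

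*Combined protocol and SAP*

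**What the plan says.** Table 5 (section D6u) has six rows, and its caption assumes "at least a medium interaction effect (f^2) for the three planned Treatment Condition X Mediation effects tests". The first three size the mediation tests with r = 0.30 for paths a and b. The last three size the Treatment Condition X Mediation tests at f² = 0.15, alpha 0.013, 0.010 and 0.008 and power 0.80, giving 93, 98 and 102 participants against 240 planned. Both kinds of effect are labelled medium. On method, "Power calculations for the interaction (mediated moderation) analyses were conducted using G*Power3 with the same assumptions". The planned sample rests on a "goal of obtaining complete data for 240 participants ($n = 80$ per condition").

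D6u supports its other inputs with data. For mechanism against pain interference it cites r = 0.57 for catastrophizing and r = -0.30 and -0.35 for mindfulness. It cites nothing for the interaction f².

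Hypothesis 1c (section A2a) states the pattern that specificity would take, for example "cognitive content (i.e., pain catastrophizing) in CT but not in MM or AS". It gives no correlation for the target arm. D6u closes by saying that the approach "has left us well-powered to detect the hypothesized effects".

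**The concern.** An interaction f² and a path correlation are on different scales, so calling both medium does not make them compatible. Once the Hypothesis 1c pattern is specified, the arm-specific slopes determine f². A modest correlation confined to one of three arms yields a small interaction, because the variance of slopes across arms is diluted by the two arms with none.

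Shared versus specific mechanisms is the primary scientific question. If the interaction tests have far less power than Table 5 suggests, a null interaction could be the likely result even when Hypothesis 1c is true. A reader relying on Table 5 might then take that null as evidence for shared mechanisms.

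**Working it through.** **Inputs.** Alpha, power, f² and required n are from Table 5. N = 240 with 80 per arm is from D6u. The numerator df of 2 is not stated in D6u; it follows from D6s, where treatment condition "is represented by two variables". The r ≥ .30 floor and the cited r values are from D6u; the pattern is from Hypothesis 1c.

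**Reproducing Table 5.** Noncentral F test with λ = f²·N, df1 = 2, df2 = N − 6 (two treatment dummies, mediator, two products). With f² = 0.15, the smallest N giving 80% power is 93, 98 and 102 at alpha .013, .010 and .008, exactly as printed (achieved power .802, .803, .803). With 1 df the answers are 78–86 and with 3 df 104–114, so 2 df is what was used. At N = 240, f² = 0.15 implies power of 99.8–99.9%.

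**From arm slopes to f².** Take mediator and outcome as standardized within arm, with equal arms. Let r_t be the target-arm correlation and r_o the correlation in each other arm. Then:

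- variance of slopes = 2(r_t − r_o)²/9
- mean squared slope = (r_t² + 2r_o²)/3
- f² = variance of slopes / (1 − mean squared slope)

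For r_t = .30 and r_o = 0: variance = 2(.09)/9 = .0200, mean squared slope = .09/3 = .03, f² = .0200/.97 = .0206.

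**What f² = 0.15 requires.** With r_o = 0, solving (2/9)r² = .15(1 − r²/3) gives r = √(.15/(2/9 + .05)) = .74.

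**Power at N = 240.**

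| r_t | r_o | f² | alpha .013 | .010 | .008 |
|---|---|---|---|---|---|
| .30 | 0 | .0206 | 29% | 26% | 24% |
| .35 | 0 | .0284 | 43% | 39% | 37% |
| .57 | 0 | .0810 | 94% | 93% | 92% |
| .57 | .165 | .0417 | 64% | 60% | 57% |
| .57 | .30 | .0195 | 27% | 24% | 22% |

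The value .165 makes the average slope (.57 + 2 × .165)/3 = .30, matching path b in Table 5 if that is a whole-sample value. A simulation of 20,000 trials for the first row gave 29.0, 25.8 and 23.3%.

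**Sample size and detectable effect.** For the first row, 80% power needs N = 645, 678 and 706. At alpha .05 its power at N = 240 is 49%. At N = 240 the smallest f² detectable with 80% power is .056, .059 and .061. With r_o = 0, r = √(f²/(2/9 + f²/3)) gives a one-arm r of .48, .49 and .50.

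**The case against.** A reader might infer that Table 5 contains an arithmetic error, or that its stated 80% is in truth 24–29%. Neither is supported. The table reproduces exactly for its stated input. Its 80% belongs to n = 93–102, whereas 24–29% is for N = 240; at 240 the plan's own input implies about 99.8%.

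The strongest defence is that the protocol never states r = .30 in one arm. That value is a floor for the path effects, and Hypothesis 1c supplies a pattern without a size. Slopes of .30, 0 and 0 average .10, which does not match path b = .30 in the first three rows. Hypothesis 1c also expects each mechanism to predict the outcome significantly, and a pooled r of .10 at N = 240 has only 20–34% power at alpha .017–.05. With the cited r = .57 in one arm and none elsewhere, power is 92–94%. All of this stands, and it rules out prescribing f² = .02 as the one correct input.

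It does not rescue 0.15. The r = .57 comes from a study of four psychosocial treatments and correlates pre-to-post changes over the same period; D6u does not describe it as specific to CT or as early change predicting later change. It concerns catastrophizing only. The mindfulness values of .30 and .35 give 24–43% even with nothing in the other arms, and D6u cites no association for activity level. Any association remaining in the other arms lowers power further.

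Two further points stand in part. Under a step-up procedure the operative alpha can exceed .008–.013, but even at .05 power at the floor is 49%. More substantively, D6s lists the six primary tests as three group differences in early mechanism slopes and three b coefficients. Its rule for supporting the Specific Mechanisms Model uses those with post hoc tests and names no treatment-by-b test. Figure 3 is not available here, so a drawn path cannot be excluded. It therefore does not follow that the D6s rule would fail to find specificity; what follows is that D6u and D6s describe different tests.

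**Conclusion.** The concern holds as an underived assumption that does not fit the plan's other inputs. Under the Hypothesis 1c pattern, f² = 0.15 needs a target-arm r of about .74, beyond the .57, -.30 and -.35 that D6u cites, and it is about seven times the f² produced by r = .30 in one arm (.15/.0206 = 7.3). At that floor, power at N = 240 is 24–29% and 80% power needs 645–706 participants rather than 93–102. The claim of being well powered for the hypothesized effects is therefore not supported at the plan's stated minimum effect.

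The size depends on a 2-df test, equal arms of 80, slopes standardized within arm, and Table 5's alphas. It is sensitive to the target-arm r and to what remains in the other arms: the scenarios above run from 22% to 94%. The documents do not support treating any single figure in that range as the trial's true power.

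**What to change.** 1. In Table 5, replace the three bare f² = 0.15 rows with f² derived from stated arm-specific slopes. Show power at N = 240 for target-arm r from .30 to .57, with both zero and non-zero slopes in the other arms.
2. State the detectable one-arm r at N = 240: about .48–.50 with none elsewhere.
3. Limit the well-powered statement in D6u to the effects for which the revised table supports it.
4. Report the specificity tests with confidence intervals, and say in advance that a null interaction will not be read as support for shared mechanisms.
5. Reconcile D6u with D6s. Either name the treatment-by-mediator interaction among the primary tests and place it in the multiplicity procedure, or power the between-group slope comparisons that D6s lists.

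The cost is one table and some wording. No extra patients are needed; the downside is a less favourable stated power.
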